7.3.4 Safety Analyses

Safety measures will be analyzed using the safety population. Medical Dictionary for Regulatory Activities (MedDRA) nomenclature will be used to code adverse events. The treatment-emergent adverse events will be summarized for randomized study treatment phase. In addition, treatment emergent adverse events attributed to 0.1% AGN-195263 treatment will be summarized for randomized study treatment phase and open-label treatment extension phase by the treatment received during the randomized study treatment phase and combined. This analysis will be performed for the subset of safety population who received 0.1% AGN-195263 during the study. Incidence rates for each treatment-emergent adverse

event will be summarized separately by (1) preferred term, (2) by primary system organ class and preferred term, and (3) by primary system organ class, preferred term and maximum severity. Summary tables will be generated for all treatment-emergent adverse events regardless of causality as well as for those considered to be treatment-related.

Detailed methods for the analyses of safety variables will be described in the AP.

7.4 Subgroup Analyses

Subgroup analyses will be performed for the primary and secondary efficacy variables by baseline overall ocular discomfort score (1, 2 to 3), baseline TBUT(≤ 2 , > 2 to ≤ 4.5 , > 4.5 to ≤ 7 , and > 7), age group, gender, and race.

7.5 Pharmacokinetic Analysis

Pharmacokinetic analysis will be performed on AGN-195263 treated patients only for post drug treatment analysis. To enable only bioanalysis of samples from patients who receive active AGN-195263 treatment, the randomization codes will be made available based on Allergan internal procedures. [REDACTED]

[REDACTED] If the serum concentrations of a given analyte are measurable, pharmacokinetic parameters, including peak or maximum drug concentration (C_{max}), time to achieve the peak concentration (T_{max}), and the area under the concentration-time curve from time 0 (baseline, prior to study treatment administration) to time of last quantifiable concentration (AUC_{0-last}), will be calculated for individual patient concentration and time profiles using standard model-independent techniques. Descriptive statistics (eg, mean, standard deviation), if applicable, will be computed for all pharmacokinetic parameters calculated.

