2.1 Study Objectives

- To evaluate the safety and efficacy of 0.1% AGN-195263 administered twice daily compared to its vehicle in patients with EDE
- To evaluate the systemic pharmacokinetics of 0.1% AGN-195263 administered twice daily in patients with EDE

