Vehicle Run-in Visit (day -14): All patients will enter a 2-week, patient-masked run-in on vehicle, where 1 drop of 0.1% AGN-195263 vehicle will be administered twice daily (morning and evening, spaced approximately by 12 hours) in each eye.

Baseline Visit (Randomization to Study Treatment and Initiation of Twice Daily Dosing [day 1]): Patients will be randomized on day 1 to receive either 0.1% AGN-195263 or its vehicle, administered as a single drop, twice daily (morning and evening, spaced approximately by 12 hours) in each eye. Both patient and investigator will be masked.

Month 1 Visit: Office visit during the randomized study treatment period. For selected patients, blood sample collection for systemic pharmacokinetics will occur (at same time \pm 1 hour of pre-dose blood sample collection at the standardization (day -21) visit) prior to in-office administration of study treatment and for 12 hours after administration of study treatment at the following intervals: 5 ± 1 min; 10 ± 1 min; 30 ± 5 min; 2 hrs \pm 15 min; 4 hrs \pm 30 min; 6 hrs \pm 30 min; 12 hrs \pm 30 min. Following the 12 hour sample collection, site staff will remind patient to administer 1 drop of study treatment in each eye prior to leaving site.

Month 3 Visit: Office visit during the randomized study treatment period. For selected patients, a single blood sample collection for systemic pharmacokinetics will occur (at same time \pm 1 hour of pre-dose blood sample collection at the standardization (day -21) visit) prior to in-office administration of study treatment.

Month 6 Visit: Primary and secondary efficacy will be assessed at the month 6 visit, after which the open-label treatment extension period starts. All patients will receive 0.1% AGN-195263, administered as a single drop, twice daily (morning and evening, spaced approximately by 12 hours) in each eye. Both patient and investigator will be unmasked. For select patients, blood sample collection for systemic pharmacokinetics will occur (at same time \pm 1 hour of pre-dose blood sample collection at the standardization (day -21) visit) prior to in-office administration of study treatment and 10 ± 1 min after administration of study treatment.

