8.3.5 Month 1 Visit (\pm 5 days)

Patients will be instructed to not administer morning dose of study treatment the day of a study visit. In addition, patients will be asked to refrain from use of SAT for 1 day prior to each study visit. One day prior to each study visit begins on the morning of the day before the study visit and continues until the end of the study visit.

The following procedures and assessments will be performed during the month 1 visit:

- Concomitant medications. Ensure to query use of:
 - Lid hygiene (ie, warm compress, lid massage, lid scrub)
 - SAT
 - Any artificial tear products other than SAT
 - Oral or topical macrolides, tetracyclines, tetracycline derivative drugs
- Hair evaluation

- Visual acuity
- Biomicroscopy (includes upper and lower lid margin appearance evaluation)
- TBUT
- Sodium fluorescein corneal staining (Oxford scheme)
- Sodium fluorescein conjunctival staining (Oxford scheme)
- At least 10-minute wait
- Schirmer's tear test with anesthesia

- IOP
- Contact IxRS
- Blood and urine sample collection for hematology, blood chemistry, PSA measurement, and urinalysis
- Pre-dose blood sample collection for pharmacokinetic analysis (testosterone, DHT, SHBG) (performed for selected patients); time of the collection should align \pm 1 hour to the pre-dose collection performed at the standardization (day -21) visit.
- In-office administration of study treatment (If patient is not participating in pharmacokinetic blood draws, time of in-office administration should be scheduled to align to the baseline (day 1) administration time of day \pm 1 hour. For all patients participating in blood sampling for pharmacokinetic analysis, study treatment should be administered at approximately the same time of day during each office visit and within 10 min after the time the pre-dose blood sample collection was performed at the current visit)
- Post-dose blood sample collection for systemic pharmacokinetics (5 minutes \pm 1 minute, 10 minutes \pm 1 minute, 30 minutes \pm 5 minutes, 2 hours \pm 15 minutes, 4 hours \pm 30 minutes, 6 hours \pm 30 minutes and 12 hours \pm 30 minutes) (for selected patients)
- Adverse events
- Study treatment dispensing
- SAT dispensing
- Collect unused study treatment

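### Section 7.5 assays post-drug PK samples from active patients only, although the named analytes are endogenous, so a concurrent randomised reference already drawn goes unused

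*Combined protocol and SAP*

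**What the plan says.** Section 2.1 makes systemic exposure one of two study objectives: "To evaluate the systemic pharmacokinetics of 0.1% AGN-195263 administered twice daily in patients with EDE".

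Section 7.5 sets the analysis set: "Pharmacokinetic analysis will be performed on AGN-195263 treated patients only for post drug treatment analysis". It continues: "To enable only bioanalysis of samples from patients who receive active AGN-195263 treatment, the randomization codes will be made available", under the sponsor's internal procedures. The text that follows directly is redacted. Where an analyte is measurable, Cmax, Tmax and AUC to the last quantifiable sample "will be calculated for individual patient concentration and time profiles using standard model-independent techniques", and "Descriptive statistics (eg, mean, standard deviation), if applicable, will be computed for all pharmacokinetic parameters calculated". The visible text gives no baseline correction and no comparison between arms.

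Section 8.3.5 (month 1) names the analytes: "Pre-dose blood sample collection for pharmacokinetic analysis (testosterone, DHT, SHBG) (performed for selected patients". Section 8.3.7 (month 6) names the same three. The lists at the other visits are redacted.

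Sections 3.1 and 8.3.2 give PK patients a profile at day -21, before any study drug: one pre-dose and seven post-dose samples over 12 hours around a dose of the study artificial tear. Later pre-dose draws are matched to its clock time within 1 hour. Randomisation comes on day 1. From the month 6 visit, Section 3.1 says: "All patients will receive 0.1% AGN-195263, administered as a single drop, twice daily".

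**The concern.** Assaying only the active arm is a sensible economy for a foreign compound, because vehicle samples would read zero. It is less sensible for hormones that every patient already has. Section 1 of the protocol itself links androgen levels to age and sex, so a measurable value on treatment is not in itself evidence of absorption.

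PK patients are bled from day -21 and randomised on day 1, so vehicle patients give the same masked-phase samples as active patients. Leaving those samples unassayed gives up a randomised, concurrent reference at no saving in visits or blood. At stake is the reading of one question under the PK objective: whether serum hormone levels on treatment moved because of the drug, or would have moved anyway.

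**Working it through.** The plan states no PK sample size, precision or drift, so there is no figure to reproduce. The check is a comparison of passages, a sample count and an illustration on assumed inputs.

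**1. What each reference can show**

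| Reference in the plan | Handles | Does not handle |
|---|---|---|
| Same-day pre-dose sample (month 1: seven post-dose samples follow; month 6: one at 10 minutes) | A rise after the dose within that visit; slow drift cannot produce it | A sustained shift: the pre-dose sample is itself taken after 1 or 6 months of dosing, so subtracting it removes the shift |
| Day -21 profile, eight samples, clock-matched | Differences between patients and time of day | Change between day -21 and the later visit, from time or from the assay |
| Vehicle patients at the same visit (drawn; no post-drug assay planned) | Time trend, and assay drift if both arms are assayed alike | – |

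Gap from day -21 to month 1: about 21 + 30 = 51 days, or 7 weeks. To month 6: about 21 + 182 = 203 days, or just under 7 months.

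**2. Samples already drawn per vehicle PK patient (Sections 8.3.5 to 8.3.7)**

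Month 1: 1 + 7 = 8. Month 3: 1. Month 6 pre-dose: 1. Total 8 + 1 + 1 = 10. At about 3 mL each (Section 12.1.16), 10 × 3 = 30 mL. The 10-minute sample at month 6 is left out because it may follow the first open-label dose.

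**3. Effect of drift on the within-arm ratio (assumed range)**

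With no drug effect and a drift of d, the expected ratio of the later value to day -21 is 1 + d: 1.05, 1.10 or 1.20 for d = 5%, 10% or 20%. If drift is the same in both arms, the active-to-vehicle ratio of these ratios is 1.00. No document supplies d.

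**4. How often drift alone would look like a change (assumed numbers)**

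Let n be the PK patients on active (half the PK subset), and δ the drift in SDs of within-patient change. With no drug effect, the chance that a 95% interval for mean change in the active arm excludes zero is Φ(δ√n − 1.96) + Φ(−δ√n − 1.96). Half-widths are 1.96/√n within arm and 1.96√(2/n) between arms, in SD units.

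| PK patients | n active | δ = 0.25 | δ = 0.5 | Half-width within arm | Half-width between arms |
|---|---|---|---|---|---|
| 20 | 10 | 12% | 35% | 0.62 | 0.88 |
| 40 | 20 | 20% | 61% | 0.44 | 0.62 |
| 80 | 40 | 35% | 89% | 0.31 | 0.44 |

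The between-arm interval excludes zero 5% of the time in every row. Its price is a width √2 = 1.41 times as large. The plan tests nothing here, so these percentages describe how a descriptive interval could mislead, not a type I error of the trial.

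**The case against.** The best defence is that the PK objective is not comparative. Section 2.1 attaches the vehicle comparison to safety and efficacy only, and Section 7.5 is descriptive. The within-patient references are also good: a post-dose rise at month 1 can be read against that morning's pre-dose sample, and the day -21 profile controls for patient and clock time. Table 4 also prohibits androgen and anti-androgen use throughout, which removes one source of change. All of this stands, and it confines the point to slow shifts in pre-dose level and in uncorrected Cmax and AUC.

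Redaction also counts. Blacked-out text sits beside the key sentence and may cover baseline handling, and an analysis plan is to be approved before the first lock. The point is therefore judged on the visible text.

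A reader might infer more than the documents support:

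- That day -21 is the only reference, or that any trend would be read as absorption. The same-day pre-dose samples rule out both.
- That releasing the codes biases the trial. Nothing says they reach sites or patients, and the primary endpoint is patient-reported. Timing and recipients are not visible, but the text around them is redacted.
- That hormone exposure drives the reading of PSA and hair findings. No visible text says so, and those measures are collected in both arms.
- That former vehicle patients lose their month 6 pre-dose reference. This is possible but unclear, because the restriction is worded for post-drug analysis and every patient is to receive active from month 6.

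**Conclusion.** The point holds in a limited form. As written, Section 7.5 leaves unassayed a randomised concurrent reference for endogenous analytes, and the remaining references cannot attribute a sustained shift to the drug. This affects the interpretation of a stated objective, not the primary or secondary efficacy tests.

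The firm figures are the 10 samples and about 30 mL per vehicle PK patient. The rest depends on assumptions: a drift of 5% to 20%, or 0.25 to 0.5 SD; 20 to 80 PK patients split equally by arm; drift equal in both arms; and the same analytes at day -21 and month 3 as at months 1 and 6. If real drift is negligible, little is lost, but without vehicle values the report could not show that. It is a worthwhile, inexpensive improvement.

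**What to change.** In Section 7.5, extend bioanalysis to the masked-phase samples of vehicle PK patients: the eight at month 1, the one at month 3 and the pre-dose sample at month 6, with the laboratory masked to arm. State that the day -21 samples of both arms are assayed, since change from day -21 needs them. Report change from day -21 at months 1, 3 and 6 by arm, and the active-minus-vehicle difference, descriptively and alongside the planned active-arm parameters. Say whether former vehicle patients' month 6 pre-dose value will serve as a reference for their later on-drug samples. Run each patient's samples in one batch only where sample stability allows; the documents give no stability data.

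The cost is 10 more assayed samples per vehicle PK patient, plus up to 8 from day -21 if those were not going to be assayed (at most 18). The between-arm interval is about 1.4 times as wide as the within-arm one, and both can be shown. No visit, draw or site staff is added, and codes are no longer needed to select these samples.

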7.6 Sample Size Calculation

The total number of patients planned for this study is 527 patients including an estimated 10% attrition rate. The sample size was estimated based on the primary efficacy analysis to compare the proportion of patients with complete overall ocular discomfort response (defined as overall ocular discomfort score equals 0) at Month 6.

Based on the final analysis of an Allergan phase 2 study (protocol 195263-006), the observed proportion of patients with complete overall ocular discomfort response over a 7-day average is 20.0% vs 9.8% (between-group difference of 10.2%) for 0.1% AGN-195263 versus vehicle, respectively. A total of 237 patients per treatment group will achieve 85% power with type I error rate of 0.05 to detect a between-group difference of 10.2% in the proportion of patients with complete overall ocular discomfort response at Month 6. This is based on the two-sided z-test (pooled variance with continuity correction), as implemented in the commercial software, [REDACTED] [REDACTED] [REDACTED] [REDACTED]. Accounting for an anticipated attrition rate of 10%, enrollment of a total of 527 patients at multiple sites is planned.

7.7 Interim Analyses

There will be no interim analysis.

8. Study Visit Schedule and Procedures

This study will be comprised of a 6-month double-masked treatment phase followed by a 6-month open label treatment extension phase evaluating safety, efficacy, and systemic pharmacokinetics of 0.1% AGN-195263 in patients with EDE. There will be 9 study visits: screening (day -51), standardization (day -21), vehicle run-in (day -14), baseline (randomization, day 1), months 1, 3, 6, 9, and 12/study exit. See [Table 1](#) for a schematic of the schedule of visits and procedures and [Figure 1](#) for schematic diagram of the study design.

[figure not shown]
8.1 Patient Entry Procedures

8.1.1 Overview of Entry Procedures

Prospective patients as defined by the criteria in [Sections 4.3](#) and [4.4](#) (inclusion/exclusion criteria) will be considered for entry into this study.

8.1.2 Informed Consent and Patient Privacy

The study will be discussed with the patient and a patient wishing to participate must give informed consent prior to any study-related procedures or change in treatment. The patient must also give written authorization (US sites only), data protection consent (European sites only), and other written documentation in accordance with the relevant country and local privacy requirements (where applicable) prior to any study-related procedures or change in treatment.

8.2 Procedures for Final Study Entry

Each patient's medical and ophthalmic history as well as medication usage will be evaluated and determined to be acceptable to the investigator prior to patient enrollment in the study.

A patient is considered to have entered the study once they have met the inclusion and exclusion criteria and are assigned a study enrollment number at the enrollment visit (day 1). See [Section 5.5](#) for the method for assignment to treatment groups/randomization.

8.3 Visits and Associated Procedures

Evaluations should be performed by the same evaluator throughout the study whenever possible. If it is not possible to use the same evaluator to follow the patient, it is preferred that evaluations should overlap and the evaluators will examine the patient together and discuss findings for at least 1 visit.

The following section provides a list of procedures for each scheduled visit. Additional information on the examination procedures, equipment, and techniques for the measures listed in this section is presented in [Section 12](#). Unless otherwise specified, procedures should be performed on both eyes. The procedures listed below are recommended to be performed in the order shown unless otherwise specified. If the patient does not qualify at a study visit, the remaining procedures for that visit should not be performed.

8.3.1 Screening Visit (Day -51)

The following procedures and assessments will be performed during the screening visit:

[figure not shown]
- Informed consent/authorization
- Demographics (including height, weight)

- Inclusion/exclusion criteria review
- Medical and ophthalmic history
- Medication history/concomitant medications. Ensure to query use of:
 - Lid hygiene (ie, warm compress, lid massage, lid scrub)
 - Any artificial tear products
 - Oral or topical macrolides, tetracyclines, tetracycline derivative drugs
- Contact IxRS
- Adverse events

8.3.2 Standardization Visit (Day -21 [\pm 1 day])

The following procedures and assessments will be performed during the standardization visit:

- Inclusion/exclusion criteria review (reassessment only for patients whose screening and standardization visits are on separate days)
- Medical and ophthalmic history (reassessment only for patients whose screening and standardization visits are on separate days)
- Concomitant medications (reassessment only for patients whose screening and standardization visits are on separate days). Ensure to query use of:
 - Lid hygiene (warm compress, lid massage, lid scrub)
 - Any artificial tear products
 - Oral or topical macrolides, tetracyclines, tetracycline derivative drugs
- Vital signs (pulse rate, blood pressure)
- Hair evaluation (all patients asked to report any use of hair growth products or hair removal procedures)

- Visual acuity (manifest refraction)
- Biomicroscopy (includes upper and lower lid margin appearance evaluation)

- TBUT
- Sodium fluorescein corneal staining (Oxford scheme)
- Sodium fluorescein conjunctival staining (Oxford scheme)
- At least 10-minute wait
- Schirmer tear test with anesthesia
- Lower lid margin meibomian gland secretion evaluation
- IOP
- Ophthalmoscopy (eyes should be dilated)
- Contact IxRS
- Blood and urine collection sample for hematology, blood chemistry, PSA measurement (males only), and urinalysis
- [REDACTED]
- [REDACTED]
- In-office administration of SAT
- Post-dose blood sample collection for systemic pharmacokinetics (5 minutes \pm 1 minute, 10 minutes \pm 1 minute, 30 minutes \pm 5 minutes, 2 hours \pm 15 minutes, 4 hours \pm 30 minutes, 6 hours \pm 30 minutes and 12 hours \pm 30 minutes) (for selected patients) (To facilitate the 12 hour time course of blood draws for pharmacokinetic analysis at the standardization (day -21) and month 1 visits, sites may “split” the visit, and perform the serial blood draws at a separate visit (the “split visit”). The split visit must occur within 5 days from the scheduled visit.)
- Adverse events
- SAT dispensing

8.3.3 Vehicle Run-in Visit (Day -14 + [3 days])

Patients will be instructed to not administer morning dose of study treatment the day of a study visit. In addition, patients will be asked to refrain from use of SAT for 1 day prior to each study visit. One day prior to each study visit begins on the morning of the day before the study visit and continues until the end of the study visit.

The following procedures and assessments will be performed during the vehicle run-in visit:

- Concomitant medications. Ensure to query use of:
 - Lid hygiene (ie, warm compress, lid massage, lid scrub)
 - SAT
 - Any artificial tear products other than SAT
 - Oral or topical macrolides, tetracyclines, tetracycline derivative drugs
- Ocular symptoms questions: overall ocular discomfort, blurred vision, ocular burning
- Visual acuity
- Biomicroscopy (includes upper and lower lid margin appearance evaluation)
- TBUT
- Sodium fluorescein corneal staining (Oxford scheme)
- Sodium fluorescein conjunctival staining (Oxford scheme)
- IOP
- Contact IxRS
- In-office administration of study treatment
- Adverse events
- Study treatment dispensing
- SAT dispensing
- Collect unused study treatment

8.3.4 Baseline Visit (Randomization, Day 1)

Patients will be instructed to not administer morning dose of study treatment the day of a study visit. In addition, patients will be asked to refrain from use of SAT for 1 day prior to

each study visit. One day prior to each study visit begins on the morning of the day before the study visit and continues until the end of the study visit.

The following procedures and assessments will be performed during the baseline visit:

- Inclusion/exclusion criteria review
- Concomitant medications. Ensure to query use of:
 - Lid hygiene (warm compress, lid massage, lid scrub)
 - SAT
 - Any artificial tear products other than SAT
 - Oral or topical macrolides, tetracyclines, tetracycline derivative drugs
- Vital signs (pulse rate, blood pressure)
- Pregnancy test (females patients only)
- Hair evaluation
- [REDACTED]
- [REDACTED]
- [REDACTED]
- Visual acuity
- Biomicroscopy (includes upper and lower lid margin appearance evaluation)
- TBUT
- Sodium fluorescein corneal staining (Oxford scheme)
- Sodium fluorescein conjunctival staining (Oxford scheme)
- At least 10-minute wait
- Schirmer tear test with anesthesia
- Lower lid margin meibomian gland secretion evaluation
- IOP
- Ophthalmoscopy (during examination, eyes to be undilated)
- Contact IxRS (randomization)

[figure not shown]
- In-office administration of study treatment
- Adverse events
- Study treatment dispensing
- SAT dispensing
- Collect unused study treatment

